2.3 Rationale

This clinical trial of adjuvant therapy (immediate ventilatory support, or hypertonic saline) for Malawian children with CM is directed toward the supportive treatment of increased brain volume, and it avoids the pitfalls that have bedeviled previous trials because:

- The interventions target a mechanism recently recognized as being strongly associated with a fatal outcome, severely increased brain volume; this mechanism is self-limited in CM survivors, suggesting that supportive care or rescue therapy may be effective.

The clinical trial setting in Malawi has been transformed because, beginning in July 2017, mechanical ventilation became available in the new Paediatric Intensive Care Unit (PICU) at the Queen Elizabeth Central Hospital.

This introduces new ethical issues: mechanical ventilation cannot be withheld in patients who suffer a respiratory arrest, and ventilatory support may result in a cadre of survivors with severe neurological sequelae. Therefore, “treatment failure” (failure of the primary intervention) is defined differently in the different therapeutic arms. In Arms 2 and 3, in which participants are not randomized to immediate ventilatory support, any participants who suffer respiratory arrest and are placed on ventilators *or* who die *or* are brain dead will be classified as treatment failures. In Arm 1, the patients who are randomized to receive immediate ventilatory support, “treatment failure” is defined as brain death at any time, *or* death at 7 days, with ventilatory support withdrawn.

The hypothesis underlying this prospective, randomized clinical trial is that death in children with CM occurs when raised intracranial pressure from severely increased brain volume impairs the function of the medullary respiratory center and that interventions which reduce ICP or support ventilation will improve survival rates in CM patients.

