 - a. Given these successes and challenges and the potential beneficial effects on mortality described in Section 11.2, a study comparing two interventions to Usual Care that will answer our original research questions prior to study closure will be challenging but remains feasible. Answering the question whether mechanical ventilation or intravenous hypertonic saline decreases mortality risk in children with CM requires sing participants enrolled in the BMP observational study prior to clinical trial commencement as Historical Controls (obviating the need for randomizing high numbers of participants into the Usual Care arm)

Historical Controls:

We identified potential Historical Controls from the electronic database of the completed observational study of cerebral malaria pathogenesis. In order to minimize temporal differences between participants randomized in the clinical trial, we began our search with children enrolled in the observational study in 2017 and moved backwards in time.

Neuroradiologists affiliated with the Treating Brain Swelling clinical trial assessed the brain MRI scans on over 200 children enrolled in the observational study. These images dated from 2014-2017.

Once consensus brain volume scores on these MRI scans were assigned by the neuroradiologists, we retrieved demographic and clinical data on children who had assigned brain volume scores of 6-8 from the master Blantyre Malaria Project database. Demographic, clinical, and outcome data were compared between children enrolled in the observational study who had brain volume scores of 6-8, and children randomized in the Treating Brain Swelling clinical trial and were randomized to Usual Care with the same range of brain volume scores. Comparisons were made between the following variables: age (in months), sex, Blantyre coma score, admission glucose, admission hematocrit, admission platelet count, and outcome. Statistical analysis: Comparisons between groups were made using t-tests or Wilcoxon test (continuous variables), ANOVA (categorical variables), or chi squared tests (dichotomous variables), as appropriate.

We found no difference in the variables in question between children enrolled in the observational study who had MRI brain volume scores of 6-8, and participants randomized in the clinical trial who had MRI brain volume scores of 6-8.

Table 4. Continuous variables compared between historical controls and randomized study participants

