1. Arm 1: Usual care + immediate mechanical ventilatory support (VENT) for a maximum of 7 days, with ventilator withdrawal once brain volume has decreased (brain volume score ≤ 5) or the patient has improved clinically (modified Blantyre Coma Score ≥ 3) or the patient dies or meets criteria for severe irreversible neurologic failure.
2. Arm 2: Usual care + intravenous hypertonic saline (HPS) for a maximum of 7 days, withdrawn once brain volume has decreased (brain volume score ≤ 5) and the patient

has improved clinically (Blantyre Coma Score ≥ 3) or the patient dies or meets criteria for severe irreversible neurologic failure.

3. Arm 3: Usual care (UC); intravenous fluids, intravenous artesunate; antipyretics, anticonvulsants and blood transfusions as needed; nutritional support) for a maximum of 7 days, or until brain volume has decreased (brain volume score ≤ 5) and the patient has improved clinically (Blantyre Coma Score ≥ 3) or the patient dies or meets criteria for severe irreversible neurologic failures

Participants will remain in the study throughout their hospitalization and, in survivors, through the 12-month post-randomization follow-up visit. Children are discharged when two sequential 6-hourly blood films are free of malaria parasites, when they have been afebrile for 24 consecutive hours, and when they are able to take medications and food by mouth. Final data collection will be at 12 months post-randomization.

Stratification:

No stratification is required. The ages of retinopathy-positive CM with severely increased brain volume per MRI who survived were compared to those of participants from the same population that died. There was no difference in the age structure (data not shown, $p=0.95$).

Primary and secondary outcomes.

The primary outcome is treatment success or failure, determined within the first 7 days. Treatment success is recovery. Treatment failure is death, ventilatory rescue (for participants in Arms 2 and 3) or meeting criteria for severe irreversible neurologic failure.

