11.4 Outcomes

The primary endpoint is death within one week following randomization. In Arm 2 and Arm 3, the endpoint will include failure of the initial treatment allocation such that the patient requires rescue ventilation. Several secondary outcomes will be assessed in the trial. Table 8 gives a brief description and preferred analytic strategies. Additional details are provided elsewhere in the Protocol.

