11.6 Interim Analyses

The TBS design is a 4-stage sequential plan to compare VENT to UC on the outcome of mortality. Based on historical controls and initial randomization to UC before 2020, mortality is

assumed fixed at $p_0 = 0.28$. We test the hypothesis that mortality p in VENT is lower, i.e., we test $H_0 : p = p_0$ versus $H_1 : p < p_0$ at significance level $\alpha = .05$. VENT will be declared superior to UC, if we can demonstrate a relative risk reduction of 50% with 80% power. This needs a sample of 38 subjects.

Boundaries for the 4-stage plan are derived from the power family. Early stopping is to reject the null hypothesis. Our first interim analysis was conducted with data from the 2019-2020 malaria seasons. Observed mortality in VENT was 12.5% (2/16). The conclusion was to continue to the next stage. Our current estimate, at the end of the 2021 season is 15.8% (3/19). In accordance with the design, we must continue to the next stage (i.e., 2022 season). The revised boundary information is depicted in the figure.

Figure: Boundary plot at conclusion of stage 2

Legend: The scale is the maximum likelihood estimate (MLE) of the mortality difference (PDIFF), $\theta = p - p_0$ against the actual information level. At stage 1, observed $\theta = 0.125 - 0.28 = -0.155$, and at stage 2, $\theta = 0.158 - 0.28 = -0.122$. The rejection boundaries are not crossed.

Conditional power and predictive power

Conditional power (CP) is the power to reject the null hypothesis $H_0: \theta = 0$ at all future stages given the cumulative interim data. This calculation shows: (a) at the current estimated difference in mortality $\theta = -0.122$, CP=76.1%, (b) at zero difference in mortality, CP=18.6%, (c) at the hypothesized difference, $\theta = -0.14$, CP=82.9%. Predictive power (PP) is the posterior probability

of rejecting the null at the next stage given the current data, assuming a non-informative prior on the mortality difference. PP=66.1% at the current stage.

Based on these assessments it behooves that we proceed to stage 3.

Hypertonic saline (HPS) vs UC

We have our first sample of 3 subjects, one of whom died. Although hardly necessary, a formal analysis provides the exact 95% CI for mortality in HPS, (0.008, 0.906).

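### Neither comparison of ventilation with usual care cleanly estimates the survival effect of immediate ventilation against current usual care, which includes rescue ventilation

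*Combined protocol and SAP*

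**What the plan says.** **Composite outcome.** Section 2.3 states that failure "is defined differently in the different therapeutic arms". In Arms 2 and 3 it covers "any participants who suffer respiratory arrest and are placed on ventilators", as well as death and brain death. Section 4 repeats this: "Treatment failure is death, ventilatory rescue (for participants in Arms 2 and 3) or meeting criteria for severe irreversible neurologic failure". Section 11.4 agrees: "In Arm 2 and Arm 3, the endpoint will include failure of the initial treatment allocation such that the patient requires rescue ventilation". The VENT arm fails only on death or brain death (Section 11.4 names death alone). Table 8 lists logistic regression for this outcome.

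**Formal test.** Section 11.6 describes a "4-stage sequential plan to compare VENT to UC on the outcome of mortality", and Section 11.7 makes it the primary test. It is one-sample: "Based on historical controls and initial randomization to UC before 2020, mortality is" then taken as fixed at 0.28, with a one-sided test at 0.05, a target of 0.14 and 38 VENT children.

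**Controls.** Section 11.5 gives 64: 16 randomised to usual care in 2018-2019 and 48 historical. Of the historical scans Section 4 says "These images dated from 2014-2017".

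**Ventilation at the site.** Section 2.3 says that "beginning in July 2017, mechanical ventilation became available in the new Paediatric Intensive Care Unit". Section 4 describes the unit as still being built in 2017. Usual care in the trial now includes rescue ventilation (Section 11.1).

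**The concern.** The hypothesis in Section 2.3 concerns survival. Under the composite, a usual care child who arrests, is ventilated and recovers is a failure, while a VENT child who is ventilated and recovers is a success. A difference can therefore appear with no child's survival changed.

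The mortality test does measure death in both groups. Its weakness is the era of the comparator. If having a ventilator available for rescue saves some children, a control rate drawn mainly from children treated before that is too high for present-day usual care. A gain from ventilators being on site would then be credited to ventilating immediately.

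At stake is a claim that immediate ventilation improves survival over usual care with rescue, made from two comparisons that both lean the same way.

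**Working it through.** **1. The plan's own figure.** Inputs from Section 11.6: p0 = 0.28, p1 = 0.14, one-sided alpha 0.05, power 80%.

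n = (1.645 + 0.842)² × p1(1 − p1) / (p0 − p1)² = 6.183 × 0.1204 / 0.0196 = 37.98, so 38.

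The stated 38 reproduces, using the variance at the alternative and a single look. With exact binomial probabilities at n = 38, rejecting at 5 or fewer deaths has size 2.6% and power 55.6%. Rejecting at 6 or fewer has size 6.2% and power 72.3%.

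**2. Share of controls from before ventilation.** 48/64 = 75%. With the 4 usual care children projected for 2023 it is 48/68 = 71%.

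**3. Effect on the mortality test.** Assumptions, since the documents give no rescue or rescue-survival rates: the 48 historical children had no rescue, the 16 randomised children did, rescue cuts mortality by a fraction f, the pooled rate is 0.28, and VENT mortality equals present-day usual care.

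- Historical rate: h = 0.28 × 64 / (48 + 16(1 − f))
- Present-day usual care rate: u = h(1 − f)
- Probability of declaring VENT superior: P(X ≤ c), with X binomial(38, u) and a single look

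| f | h | u | c = 5 | c = 6 |
|---|---|---|---|---|
| 0 | 0.280 | 0.280 | 2.6% | 6.2% |
| 0.1 | 0.287 | 0.258 | 4.8% | 10.5% |
| 0.2 | 0.295 | 0.236 | 8.8% | 17.4% |
| 0.3 | 0.303 | 0.212 | 15.5% | 27.7% |

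With f = 0 there is no bias. For any f above 0 the bias favours VENT. The four-stage boundaries are not modelled here.

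**4. The comparability check.** Section 4 reports p = 0.551 for death/survival, 48 versus 16 children. By normal approximation with pooled null variance, two-sided 0.05, that test has about 6% power at f = 0.2 (0.295 vs 0.236) and 20% at f = 0.5 (0.320 vs 0.160). Unpooled variance gives about 8% and 29%. A non-significant result at that size cannot exclude the reductions in the table. Availability of ventilation is not among the variables compared.

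**5. The composite.** Its direction follows from the definition: each usual care child rescued and alive adds a failure to one arm only. The documents do not say how many there were, so no size is given.

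**6. Figures under one label.**

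| | Sections 4 and/or 11.5 | Section 11.6 |
|---|---|---|
| Usual care plus historical, called mortality | 36% (0.36 × 64 = 23.0) | 28% (0.28 × 64 = 17.9) |
| VENT, end of 2021 season | 5/19 = 26.3%, died or brain dead (Section 4) | 3/19 = 15.8%, mortality |

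The VENT minus control difference is 0.263 − 0.36 = −0.097 on the first set and 0.158 − 0.28 = −0.122 on the second. No section reconciles them.

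**7. Precision of a randomised-only comparison.** For 0.28 versus 0.14, one-sided 0.05, power is about 35% with 16 usual care and 38 VENT children. With the projected 20 and 32 it is 33% by exact enumeration and 35% by normal approximation.

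**The case against.** The arm-specific definition is deliberate and disclosed. Section 2.3 gives an ethical reason: ventilation cannot be withheld after an arrest. Failure of the allocated strategy is a legitimate thing to estimate. That stands, and it is why the composite should stay. It does not turn the composite into a measure of survival.

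Survival is not ignored. Section 9.1 makes a three-arm survival comparison the primary safety parameter, Section 11.7.2 plans joint modelling of treatment success and survival, and the Glasgow Outcome Scale includes death. But Section 9.1 gives no method and no rule on historical controls, and Section 11.7.2 is exploratory and motivated by the other two arms. The need is to specify a comparison, not to invent one.

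Two limits on the facts also stand. Sixteen of the 64 controls had rescue available. For the other 48, the lack of ventilation is inferred from dates and stated nowhere.

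A reader might go further in two ways that the documents do not support:

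- **That the gap between 36% and 28% (23 − 18 = 5 children) counts rescued survivors.** Both figures are called mortality, and VENT, which has no rescue component, shows a similar split. Brain death is at least as plausible an explanation. Large composite biases also need implausible rates: 12 points across 64 controls is 7.7 children, or 48% of the 16 randomised.
- **That deaths in randomised usual care can be recovered from p = 0.551.** A split of 16/48 versus 7/16 gives Fisher p = 0.5507, but 17/48 versus 7/16 and 19/48 versus 5/16 give 0.551 by uncorrected chi-square. The split is not identified.

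**Conclusion.** The concern holds in this form: neither comparison cleanly estimates the survival effect of immediate ventilation against current usual care with rescue, and no prespecified concurrent analysis with one definition fills the gap. Both features favour VENT.

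For the mortality test, false superiority rises from 2.6% to about 5%, 9% or 15% if rescue lowers mortality by 10%, 20% or 30%. These figures rest on the assumed reductions, on the inference that the 2014-2017 children had no ventilation, and on a single look at n = 38 with rejection at 5 or fewer deaths. For the composite only the direction is established.

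It might be inferred that the historical rate must be abandoned, or that a survival claim may rest only on the randomised children. Neither follows. Dropping the rate would undo the four-stage boundaries, the sample size and the conditional power after two stages have been run. A comparison with about 33-35% power cannot carry the claim alone. This is a change that should be made, not a reason to set the design aside.

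**What to change.** Keep the composite and the sequential design, and add the following to the statistical section:

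1. A key supporting analysis for VENT versus usual care: death or brain death within 7 days, defined identically in all arms, in randomised children only, reported as an estimate with a confidence interval.
2. A rule that any survival conclusion for VENT from the fixed-rate test or the composite is reported beside that analysis, and qualified if the two do not agree in direction.
3. A sensitivity analysis of the sequential test over lower control rates, for example 0.26, 0.24 and 0.21, which correspond to the three reductions above.
4. A reconciliation of 36% with 28% for usual care and of 5/19 with 3/19 for VENT, stating for each which events are counted and whether brain death is among them.

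The cost is statistical wording and analyses of data already being collected. No treatment, enrolment or boundary changes. The downside is imprecision: with 16 to 20 randomised usual care children the supporting analysis will have a wide interval, so a survival conclusion for VENT may have to be worded more cautiously.

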ventricular reservoir during ventricular taps and ventriculoperitoneal shunting. Resistive index decreased significantly from a mean of 0.9 pre-CSF removal to 0.75 post-CSF removal.²⁰⁹ In another 22 infants with hydrocephalus and a ventricular reservoir, a volume of 5ml/kg body weight was removed twice daily and ICP and TCD flow velocities were determined before and after CSF tapping.⁷ A significant decrease in ICP after CSF removal was accompanied by a concomitant increase in mean flow velocity ($p < 0.05$) and Vd ($p < 0.01$). A significant decrease in resistive index was also noted ($p < 0.01$). The current expert consensus is that a $\geq 10\%$ change in Vd or PI represented a clinically meaningful change to ICP ([name] personal communication).

Heart rate variability (HRV) patterns: Heart rate is the net result of complex interactions at every level of the organism and these interactions are severely impacted by critical illness. Ultimately, heart rate, strength of cardiac contraction and vascular resistance are regulated on a beat-by-beat basis in order to optimize cardiac output to the needs of the body (resulting in healthy HRV). A primary mediator of heart rate is the autonomic nervous system which directly innervates the sino-atrial node (the heart's pacemaker). In healthy individuals, the autonomic nervous system is responsive to the needs of the body, *i.e.*, heart rate accelerates with inhalation and decelerates with respiration (respiratory sinus arrhythmia) and also changes at a slower rate in association with oscillations in the baroreflex and other physiologic rhythms, as well as in response to external stimuli. It has been clearly shown that there is a loss of normal HRV in the presence of critical illness and that it returns in association with clinical improvement²¹². Although nothing is known about the evolution of HRV in CM, we postulate that HRV will be diminished and possibly disorganized (lacking the expected intrinsic rhythms), and that potentially HRV will be significantly worse in CM with brain swelling compared to CM without it. Furthermore, it would be expected that HRV will improve in association with underlying clinical improvement. In order to test these hypotheses, we will use monitors to record the EKG in all children for at least 24 hours. These data will be downloaded for off-line analysis. HRV will be obtained from a beat-to-beat file generated by research scanning of the EKG signal and then examined in multiple ways:

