1. A tachogram of instantaneous heart rates *vs.* time will be plotted. That will permit identification of the presence of any HRV and the evolution of regular respiratory sinus arrhythmia and other trends in heart rate patterns as the patient's condition evolves or interventions are undertaken.
2. Heart rate and multiple HRV parameters will be calculated for every 2 minutes of the recording period and their evolution plotted over time. They will reflect how much HRV there is, the underlying oscillatory rhythms in the HRV pattern and the relative organization *vs.* randomness of heart rate patterns. These parameters can also be averaged over longer periods of time for statistical purposes.

Biobanking: Admission samples of plasma, urine and CSF will be bio banked for later analysis, via a separate funding source. The most widely studied of biomarkers in pediatric brain injury include S100B, neuron specific enolase (NSE), and myelin basic protein (MBP)²¹³. Although the neuropathological role of these biomarkers is incompletely understood^{214, 215}, they have

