The secondary outcomes include rates of neurological sequelae in all 3 groups; potential surrogate measures of increased intracranial pressure (opening CSF pressure, ONSD measurements from serial ultrasound examinations, NIRS measurements of cerebral oxygenation and muscle reperfusion, serial examinations for papilledema, decreased diastolic flow velocity or increased pulsatility index on TCD, heart rate variability patterns from continuous cardiac monitoring measured from enrollment through initial MRI scan, and standardized clinical observations) and development of hypotension following induction/intubation, defined by proportional deviation from the initial systolic blood pressure at enrollment.

Data collection methods.

The primary outcome will be determined by study clinicians.

For secondary objectives, the following methods will be used:

- ONSD measurements will be collected at the bedside. Data will be transferred to the electronic case report form (CRF).

- TCD measurements will be collected at the bedside. Data will be transferred to the electronic case report form (CRF).
- NIRS will be used to record cerebral oxygenation fluctuations and to measure muscle reperfusion rates after transient occlusion.
- The evolution of heart rate variability and its relationship to clinical status and outcomes will be determined by extracting the archived and time-stamped continuous ECG signal.
- The neurological findings will be captured by clinicians on an electronic case report form (CRF) at the bedside.
- Neurologic status at the 1, 6, and 12-month post-randomization follow-up will be assessed by one of two pediatric neurologists or clinicians trained by them. The Glasgow Outcome Scale (GOS), a global scale for functional outcome that rates patient status into one of five categories (dead, vegetative state, severe disability, moderate disability or good recovery)²⁴⁷ will be used.. Study nurses will administer standardized assessments: The Malawi Developmental Assessment Tool (MDAT) for participants up to the age of 59 months; the Kaufman Assessment Battery for Children, Version II (KABC-II), for participants over the age of 59 months. Both have been validated for use in African children ^{248, 249}.

The details of the techniques involved for the specialized assays (funduscopy, MRI, ONSD, TCD, NIRS, heart rate variability) are included in Section 8 of this Protocol.

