6.7 Dosage, Preparation and Administration of Study Intervention/Investigational Product (VENT)

Mechanical ventilation will be initiated immediately after randomization to Study Arm 1, or in the event of a respiratory arrest for subjects allocated to Arms 2 and 3.

Endotracheal intubation will be performed by a pediatric intensivist after administration of IV anesthetic agents in doses described in the sedation section (Section 6.3). The size of the endotracheal tube to be used for each patient will be determined by the pediatric intensivist on-site using standard formulas. A variety of sizes of both cuffed and uncuffed endotracheal tubes will be available (ranging from size 3.0 to 7.5) along with laryngoscopes and different sizes of blades

At the discretion of the intensivist, initial ventilator settings may be set to deliver a Tidal Volume at 6-8 ml/kg, age-appropriate respiratory rate, Peak End Expiratory Pressure of 5 and Fraction of Inspired Oxygen at 40%. The settings will be adjusted by the pediatric intensivists to target a pCO₂ (partial pressure of carbon dioxide) in arterial blood of 35-40 mmHg and maintain oxygen saturation above 90% on pulse oximetry.

At the discretion of an intensivist, an arterial line may be placed in the ventilated subjects to measure arterial blood gases every 3 hours for the first 24 hours and every 6 hours subsequently until the participant is extubated.

Participants will remain intubated until brain volume has decreased (brain volume score \leq 6) and the participant has improved clinically (modified Blantyre Coma Score \geq 3) or the patient has improved clinically (modified Blantyre Coma Score \geq 4, no repeat MRI needed) or the patient dies or develops severe irreversible neurologic damage or for a maximum of 7 days.

Intubated participants will be moved from side to side every 2 hours (\pm 1 hour) to reduce chances of bed sores. If tolerated, they will undergo endotracheal suctioning every 6 hours (\pm 2 hours) and more often as needed to prevent plugging of the endotracheal tube by mucoid secretions, using an appropriate sized suction catheter attached to wall suction. Participants may be pre-medicated prior to suctioning using sedation medications described in section 6.3.

Participants will receive chest physiotherapy as needed if they develop evidence of lung atelectasis. They may be premedicated with sedation medications as described in section 6.3.

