8.3.6 Heart rate variability

When patients are admitted or transferred to the PICU, they are connected to bedside monitoring which includes electrocardiogram (EKG), respiration waveforms, oxygen levels, and blood pressures. The ICU monitors display instantaneous values for these clinical parameters and plots of their trends. These waveforms will be archived, compressed and uploaded for offline analysis of patterns of heart rate variability and integration of results with the clinical course. A 60 minute reading will be taken in the supine position. Readings will undertaken every six hours for the first 24 hours of admission, then daily until the patient's Blantyre Coma Score is ≥ 3 , and again upon discharge. The aim is to undertake the recordings at the same time every day; currently 0600, 1200, 1800 and 0000. Readings will be discontinued upon death or improvement of Blantyre coma score to ≥ 3 .

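### The HRV recording window is defined inconsistently, and only one version keeps study treatment out of the swollen-versus-unswollen comparison

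*Combined protocol and SAP*

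**What the plan says.** Section 2.3 proposes HRV as one of several bedside surrogates for increased brain volume. It states two expectations: "potentially HRV will be significantly worse in CM with brain swelling compared to CM without it", and "it would be expected that HRV will improve in association with underlying clinical improvement". It continues: "In order to test these hypotheses, we will use monitors to record the EKG in all children for at least 24 hours". On processing it says "Heart rate and multiple HRV parameters will be calculated for every 2 minutes of the recording period", and on summarising, "These parameters can also be averaged over longer periods of time for statistical purposes".

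Section 4, in its list of secondary outcomes, gives a narrower measure: "heart rate variability patterns from continuous cardiac monitoring measured from enrollment through initial MRI scan".

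Section 8.3.6 gives a third description: "A 60 minute reading will be taken in the supine position", repeated six-hourly for the first day of admission, then daily until the Blantyre Coma Score reaches 3, and once more at discharge. Table 8 (Section 11.5) lists HRV as a continuous outcome for linear regression, with repeated-measures analysis of serial values, and states no window. Appendix A first marks HRV in the column for trial consent and has no mark under admission or screening.

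On the start of treatment, Section 6.7 says "Mechanical ventilation will be initiated immediately after randomization to Study Arm 1".

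**The concern.** Randomisation is open only to children with a brain volume score of 6 or more (Section 5.1), so randomised treatment occurs only in the swollen group. Section 2.3 itself explains that heart rate varies with breathing and with the baroreflex. Ventilation, the ketamine and diazepam used at intubation (Section 6.11) and the volume expansion attributed to hypertonic saline (Section 2.2.2.4.4) can therefore plausibly change HRV directly. If the HRV values compared between swollen and unswollen children come from after randomisation, swelling and treatment are mixed.

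This matters because Secondary Objective 2 is meant to find markers that can stand in for MRI where there is no scanner. A marker that partly detects that a child is ventilated or sedated would not serve that purpose. The recovery hypothesis has a related difficulty: Sections 4 and 6.7 tie withdrawal of the interventions to clinical improvement, so recovery and the end of treatment tend to coincide.

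**Working it through.** The plan gives no sample size, effect or standard deviation for the HRV comparison, so it has no figure to reproduce. The check sets the windows side by side and then counts who is treated.

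**1. The windows**

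| Place | HRV window | Ends before study treatment? |
|---|---|---|
| Section 4, secondary outcomes | Enrollment to initial MRI | Yes |
| Section 2.3 | At least 24 h; longer averaging allowed | Not stated |
| Section 8.3.6 | 60-min readings at fixed clock times for 24 h, then daily | No |
| Table 8 | Serial, no window | Not stated |
| Appendix A | First mark at trial consent | No; starts after the MRI |

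**2. Order of events**

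The MRI is part of screening (Sections 5.1 and 7.1). Consent for the trial is sought after the MRI (Section 7.2), randomisation follows screening (Section 5.3.1), and ventilation follows at once (Section 6.7). The Section 4 window therefore contains no study treatment.

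Two things leave that window unsecured. Section 7.2 places trial enrollment after the MRI, so the window is empty unless enrollment in Section 4 means entry to screening. And Appendix A marks no HRV recording before trial consent, while the fixed clock times in Section 8.3.6 do not guarantee a reading before the MRI.

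**3. Share of randomised swollen children on an active arm**

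f = (VENT + HPS) / (VENT + HPS + randomised UC). The 48 historical controls are left out because they were not recorded in this trial. Randomised UC in the projected-enrollment table of Section 4 is 68 − 48 = 20.

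- 2018-2019: 16 / (16 + 16) = 50%
- To the end of 2021: (19 + 3) / (19 + 3 + 16) = 22/38 = 58%
- Projected total: (32 + 32) / (32 + 32 + 20) = 64/84 = 76%
- Against the planned 128: 64 / (128 − 48) = 64/80 = 80%

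Swollen children whose caregivers decline randomisation are also monitored for HRV (Section 4) and are not on a trial arm. Their number is not given. If a share q of eligible swollen children declines (an assumption), the projected share becomes 64/84 × (1 − q): 69% at q = 10%, 61% at 20% and 53% at 30%.

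**4. What can be said about bias**

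For an unadjusted mean over the recording, with unswollen children untreated:

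bias = f × w × δ

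Here w is the share of the recording made after treatment starts and δ is the shift in HRV caused by treatment. Only f can be taken from the documents. For the projected 84 randomised children the bias is at most 64/84 × δ = 0.76δ if both interventions shift HRV equally, or 32/84 × δ = 0.38δ if only ventilation does. Both figures take w = 1. In the Section 4 window w = 0, so the bias from study treatment is 0 whatever δ is.

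**5. Whether the model removes it**

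Section 11.7 puts an arm indicator (VENT, HPS, UC) in the covariates for the 128 children across the three arms. Screened children who were never randomised have no arm and are not in that set. No model is specified for comparing them with the swollen children.

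**The case against.** The best defence is that Section 4 is where the surrogate HRV measure is defined as an outcome, and its window is clean. Section 2.3 is rationale. It gives a recording length that serves two hypotheses together, and the recovery one needs a long recording. HRV at two-minute resolution lets a pre-treatment segment be separated, and Sections 2.3 and 4 both show that later HRV is expected to be read in relation to interventions. The remark about longer averaging is a permission, not a planned contrast.

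Much of this stands. A reader might infer that the swelling test uses the full 24 hours, so that a treatment effect will be taken for a swelling effect. The documents do not say so. Untreated swollen children, in the usual-care arm and among decliners, would also dilute any bias, and half of those randomised in 2018-2019 were on usual care. Anticonvulsants with sedating effects are available to any child (Section 6.11), so drug effects are not confined to the ventilated arm.

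What does not stand is that Section 4 settles the matter. The measurement section, the analysis table and the schedule do not repeat its window, the schedule provides no recording in it, and the word enrollment has to be read in one particular way for it to exist.

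**Conclusion.** The inconsistency is real and should be resolved before the surrogate analysis. If the comparison follows Section 4, study treatment contributes no bias. If it follows the schedule, or averages the long recordings, it mixes swelling with treatments that a projected 76% of randomised swollen children receive (50% in 2018-2019, and down to 53% of all swollen children if an assumed 30% decline).

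The size of any distortion cannot be stated, since the HRV effect of treatment, its standard deviation and the time from admission to randomisation are all absent. A false-positive rate would rest on guesses for each of these and on the number of unswollen children. The 67 children screened but not randomised in 2018-2019 ((57 − 8) + (42 − 24)) cannot supply that number, because they may include decliners and children with score 6 from 2018.

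Nor does the point carry over to transcranial Doppler, NIRS or the neurological signs. A reader might want the same cut there, but it would discard planned daily measurements that can be paired with the daily MRI. The point concerns one secondary surrogate and does not touch the primary outcome.

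**What to change.** - In Sections 2.3 and 8.3.6 and in Table 8, state that the swollen-versus-unswollen HRV comparison for Secondary Objective 2 uses only ECG recorded before randomisation, in the Section 4 window, and define enrollment there as entry to screening. Unrandomised children have no randomisation time, so the initial MRI is the natural end point for both groups.
- In Appendix A, mark HRV at admission or screening for all screened children. This fits the monitoring already intended for all children in Section 2.3, for decliners in Section 4, and for the first 24 hours in Section 14.4.
- Analyse later HRV separately for the recovery hypothesis, with arm and current ventilation and sedation status in the model. Because withdrawal of treatment is tied to improvement, this adjustment may not separate the two fully, and the report should say so.

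The cost is a few sentences and a schedule entry. For children already enrolled, a time filter on the archived, time-stamped signal is enough only where ECG was recorded before the MRI. The statistical price is shorter recordings, and so noisier HRV values per child.
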